### ***SAEs and AEs That Are Related to Vaccination or That Led to Discontinuation:***

At any time during the study, a subject who experiences an SAE or an AE must be followed if *either* of the following is true:

- The SAE or AE is considered by the Investigator to be related to vaccination, and is not resolved by the end of the subject's participation in the trial
- The subject has been discontinued from the trial because of the SAE or AE

Any such subject must be followed until the condition resolves, becomes stable, or becomes chronic.

#### **5.1.5 Planned Trial Calendar**

The following dates are approximate. The actual dates may differ as, for example, the trial will not start until all the appropriate regulatory and ethical approvals have been obtained.

Planned trial period - FVFS to LCLSa: 15 July 2016 - 05 May 2017

Planned inclusion period - FVFS to FVLS: 15 July 2016 – 04 November 2016

Planned end of trial: 05 May 2017

Planned date of final clinical study report: March 2018

Safety Follow-up Telephone Call (180 [+14] days after Visit 1) of the last subject in either group is considered to be the end of the trial.

#### **5.1.6 Early Safety Data Review**

This trial will not include an early review of safety data (i.e., no early safety review[s] of preliminary safety data occurring at pre-determined milestones defined in the protocol with pause in enrollment). However, it may be interrupted at any time if new data about the investigational product become available, and/or on advice of the Sponsor, the IECs/IRBs, or the governing regulatory authorities in the country where the trial is taking place.

If the trial is prematurely terminated or suspended, the Sponsor will promptly inform the Investigator's, the IECs/IRBs, and the regulatory authorities of the reason for the termination or suspension. If the trial is prematurely terminated for any reason, the Investigator will promptly inform the subjects' parents / guardian and should assure appropriate therapy and follow-up.

## **5.2 Enrollment and Retention of Trial Population**

### **5.2.1 Recruitment Procedures**

Before the start of the trial, the Investigator and / or study staff may contact subjects of an appropriate pool of potential subjects and invite them to participate in the study. The site will

---

a FVFS: First visit of first subject; LCLS: Last contact of last subject; FVLS: First visit of last subject

ensure that any advertisements used to recruit subjects (e.g. letters, pamphlets, and posters) are submitted to Sanofi Pasteur for review prior to submission to the IEC/ IRB for approval.

In addition, a subject who visits the trial site for a routine visit may be invited to enroll in the trial, if eligible. Subjects may also be recruited from the general population.

### 5.2.2 Informed Consent Procedures

Informed consent is the process by which a subject voluntarily confirms his or her willingness to participate in a particular trial. Informed consent must be obtained before any study procedures are performed. The process is documented by means of a written, signed, and dated ICF.

In accordance with GCP, prior to signing and dating the consent form, the subject must be informed by appropriate study personnel about all aspects of the trial that are relevant to making the decision to participate, and must have sufficient time and opportunity to ask any questions.

A subject who cannot read will not be included in the trial.

The actual ICF used at each center may differ, depending on local regulations and IEC / IRB requirements. However, all versions must contain the standard information found in the sample ICF provided by the Sponsor. Any change to the content of the ICF must be approved by the Sponsor and the IEC / IRB prior to the form being used.

If new information becomes available that may be relevant to the subject's willingness to continue participation in the trial, this will be communicated to him / her in a timely manner. Such information will be provided via a revised ICF or an addendum to the original ICF.

ICFs will be provided in duplicate, or a photocopy of the signed consent will be made. The original will be kept by the Investigator, and the copy will be kept by the subject.

Documentation of the consent process should be recorded in the source documents.

### 5.2.3 Screening Criteria

There are no screening criteria other than the inclusion and exclusion criteria.

### 5.2.4 Inclusion Criteria

An individual must fulfill *all* of the following criteria in order to be eligible for trial enrollment:

- 1) Aged  $\geq 56$  years on the day of inclusiona
- 2) Informed consent form has been signed and dated
- 3) Able to attend all scheduled visits and to comply with all trial procedures

---

a " $\geq 56$  years" means from the day of the 56th birthday and older

### 5.2.5 Exclusion Criteria

An individual fulfilling *any* of the following criteria is to be excluded from trial enrollment:

- 1) Subject is pregnant, or lactating, or of childbearing potential (to be considered of non-childbearing potential, a female must be post-menopausal for at least 1 year, surgically sterile, or using an effective method of contraception or abstinence from at least 4 weeks prior to vaccination until at least 4 weeks after vaccination)
- 2) Participation in the 4 weeks preceding the trial vaccination or planned participation during the present trial period in another clinical trial investigating a vaccine, drug, medical device, or medical procedure
- 3) Receipt of any vaccine in the 4 weeks (28 days) preceding the trial vaccination or planned receipt of any vaccine prior to Visit 2 except for influenza vaccination, which may be received at least 2 weeks before or after study vaccine. This exception includes monovalent pandemic influenza vaccines and multivalent influenza vaccines.
- 4) Previous vaccination against meningococcal disease with either the trial vaccine or another vaccine (i.e., mono- or polyvalent, polysaccharide, or conjugate meningococcal vaccine containing serogroups A, C, Y, or W; or meningococcal B vaccine)
- 5) Receipt of immune globulins, blood or blood-derived products in the past 3 months
- 6) Known or suspected congenital or acquired immunodeficiency; or receipt of immunosuppressive therapy, such as anti-cancer chemotherapy or radiation therapy, within the preceding 6 months; or long-term systemic corticosteroid therapy (prednisone or equivalent for more than 2 consecutive weeks within the past 3 months)
- 7) History of meningococcal infection, confirmed either clinically, serologically, or microbiologically
- 8) At high risk for meningococcal infection during the trial (specifically, but not limited to, subjects with persistent complement deficiency, with anatomic or functional asplenia, or subjects travelling to countries with high endemic or epidemic disease)
- 9) Known systemic hypersensitivity to latex or any of the vaccine components, or history of a life-threatening reaction to the vaccine used in the trial or to a vaccine containing any of the same substancesa
- 10) Personal history of Guillain-Barré syndrome (GBS)
- 11) Personal history of an Arthus-like reaction after vaccination with a tetanus toxoid-containing vaccine within at least 10 years of the proposed study vaccination
- 12) Verbal report of thrombocytopenia, contraindicating intramuscular vaccination, in the Investigator's opinion

---

a The components of MenACYW conjugate vaccine are listed in [Section 6.1.1.1](#) and in the Investigator's Brochure. The components of Menomune® – A/C/Y/W-135 are listed in [Section 6.1.2.1](#) and in the package insert. Menomune® – A/C/Y/W-135: The stoppers to the vials of lyophilized vaccine and diluent contain dry natural latex rubber that may cause allergic reactions in latex sensitive persons.

- 13) Bleeding disorder, or receipt of anticoagulants in the 3 weeks preceding inclusion, contraindicating intramuscular vaccination in the Investigator's opinion
- 14) Deprived of freedom by an administrative or court order, or in an emergency setting, or hospitalized involuntarily
- 15) Current alcohol abuse or drug addiction
- 16) Chronic illness that, in the opinion of the investigator, is at a stage where it might interfere with trial conduct or completiona
- 17) Moderate or severe acute illness/infection (according to investigator judgment) on the day of vaccination or febrile illness (temperature  $\geq 100.4^{\circ}\text{F}$ ). A prospective subject should not be included in the study until the condition has resolved or the febrile event has subsided
- 18) Receipt of oral or injectable antibiotic therapy within 72 hours prior to the first blood draw
- 19) Identified as an Investigator or employee of the Investigator or study center with direct involvement in the proposed study, or identified as an immediate family member (i.e., parent, spouse, natural or adopted child) of the Investigator or employee with direct involvement in the proposed study

If the subject has a primary physician who is not the Investigator, the site must contact this physician with the subject's consent to inform him / her of the subject's participation in the study. In addition, the site should ask this primary physician to verify exclusion criteria relating to previous therapies, such as receipt of blood products or previous vaccines.

### 5.2.6 Medical History

Prior to enrollment, subjects will be assessed for pre-existing conditions and illnesses, both past and ongoing. Any such conditions will be documented in the source document. Significant medical history (reported as diagnosis) including conditions for which the subject is or has been followed by a physician or conditions that could resume during the course of the study or lead to an SAE or to a repetitive outpatient care will be collected in the CRF. The significant medical history section of the CRF contains a core list of body systems and disorders that could be used to prompt comprehensive reporting, as well as space for the reporting of specific conditions and illnesses.

For each condition, the data collected will be limited to:

- Diagnosis (this is preferable to reporting signs and symptoms)
- Presence or absence of the condition at enrollment

The reporting of signs and symptoms is strongly discouraged.

Dates, medications, and body systems are not to be recorded, and the information collected will not be coded. Its purpose is to assist in the later interpretation of safety data collected during the trial.

---

a Chronic illness may include, but is not limited to cardiac disorders, renal disorders, auto-immune disorders, diabetes, psychomotor diseases, and known congenital or genetic diseases

### 5.2.7 Contraindications for Subsequent Vaccinations

Not applicable since only one dose of vaccine will be administered in this trial.

### 5.2.8 Contraindications for Subsequent Blood Samples

Should a subject receive oral or injectable antibiotic therapy within 3 days before the second blood draw, the Investigator will postpone that blood draw until it has been 3 days since the subject last received oral or injectable antibiotic therapy. Postponement must still be within the timeframe for blood draw (30 to 44 days after vaccination on D0). If postponement would result in the sample collection falling outside of this timeframe, the blood sample should be collected without postponement, and it should be documented appropriately that the sample was taken less than 3 days after stopping antibiotic treatment.

### 5.2.9 Conditions for Withdrawal

Subjects will be informed that they have the right to withdraw from the trial at any time. A subject may be withdrawn from the study:

- At the discretion of the Investigator or Sponsor due to safety concerns (withdrawal) without the subject's permission
- At the request of the subject (dropout)

The following will result in automatic withdrawal or exclusion of a subject from the study:

- Significant non-compliance with the protocol, based on the Investigator's judgment

The reason for a withdrawal or dropout should be clearly documented in the source documents and on the CRF.

The Investigator must determine whether voluntary withdrawal is due to safety concerns (in which case, the reason for discontinuation will be noted as "SAE" or "other AE" as appropriate) or for another reason.

Withdrawn subjects will not be replaced.

### 5.2.10 Lost to Follow-up Procedures

In the case of subjects who fail to return for a follow-up examination, documented reasonable effort (i.e., documented telephone calls and certified mail) should be undertaken to locate or recall them, or at least to determine their health status while fully respecting their rights. These efforts should be documented in the CRF and in the source documents.

### 5.2.11 Classification of Subjects Who Discontinue the Trial

For any subject who discontinues the trial prior to completion, the most significant reason for early termination will be checked in the CRF. Reasons are listed below from the most significant to the least significant (refer to the CRF completion guidelines for additional details and examples):

- **Serious adverse event:** To be used when a subject drops out of or is withdrawn from the study by the Investigator because of the occurrence of an SAE, as defined in [Section 9.3.2.1](#).
- **Other adverse event:** To be used when a subject drops out of or is withdrawn from the study by the Investigator because of the occurrence of an AE other than an SAE, as defined in [Section 9.3.2.1](#).
- **Non-compliance with protocol:** To be used when the Investigator withdraws a subject from the study because of failure to follow the protocol, including when it is retrospectively discovered that a subject did not fulfill the eligibility criteria. The Investigator will provide a comment as to the specific cause of non-compliance.
- **Lost to follow-up:** To be used when the Investigator withdraws a subject from the study because of failure to establish contact, as outlined in [Section 5.2.10](#). The Investigator will provide documentation that contact was attempted (i.e., return of unsigned certified letter receipt).
- **Voluntary withdrawal not due to an adverse event:** To be used when a subject drops out of the study for any reason other than those listed above.

### 5.2.12 Follow-up of Discontinuations

The site should complete all scheduled safety follow-ups and contact any subject who has prematurely terminated the trial because of an SAE, other type of AE, non-compliance with the protocol, or loss of eligibility, including definite contraindications.

For subjects where the reason for early termination was lost to follow-up or if the subject withdrew informed consent and specified that they do not want to be contacted again and it is documented in the source document, the site will not attempt to obtain further safety information.

For subjects where the reason for early termination is voluntary withdrawal, the site will attempt to contact them for the 6-month follow-up except if they specified that they do not want to be contacted again and it is documented in the source document.

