5.2.3 Safety Analysis Set

The SafAS is defined as those subjects who have received at least 1 dose of the study vaccine and have any safety data available. All subjects will have their safety analyzed according to the vaccine they actually received.

If the vaccine received by a subject does not correspond to any study group, the subject will be excluded from the SafAS. The corresponding safety data will be presented in separate listings.

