5.3 Handling of Missing Data and Outliers

5.3.1 Safety

No replacement will be done. In all subject listings, partial and missing data will be clearly indicated as missing.

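### Protocol 5.2.12 bars further safety contact with subjects lost to follow-up, and the SAP has no denominator or censoring rule for the SAE and MAAE time left unobserved

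*Protocol*

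**What the plan says.** **Contact after early termination (Protocol 5.2.12).** Subjects terminated for an SAE, another AE, non-compliance or loss of eligibility complete all scheduled safety follow-ups. For voluntary withdrawals, "the site will attempt to contact them for the 6-month follow-up except if they specified that they do not want to be contacted again". For subjects lost to follow-up, and for those who withdrew consent and asked not to be contacted, "the site will not attempt to obtain further safety information".

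**Effort before the label is applied.** If a subject misses Visit 2 and the diary card is not received, Protocol 5.1.4 has the site telephone. After 3 failed attempts it refers to 5.2.10, where documented calls and certified mail "should be undertaken to locate or recall them, or at least to determine their health status while fully respecting their rights". Under 5.2.11 the lost-to-follow-up category is "To be used when the Investigator withdraws a subject from the study because of failure to establish contact".

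**Collection and analysis.** Protocol 9.3.2.3.4 collects SAEs from Visit 1 to 180 days after vaccination. SAP Table 5.2 summarises SAEs to the 6-month follow-up, and MAAEs from Visit 2 to the 6-month follow-up, as proportions of subjects, for all subjects in both groups. SAP 5.2.3 sets the population: "The SafAS is defined as those subjects who have received at least 1 dose of the study vaccine and have any safety data available". For missing safety data, SAP 5.3.1 says "No replacement will be done". For solicited reactions, SAP 4.4.2.1.3 leaves subjects without data out of that endpoint. No matching rule is given for SAEs or MAAEs.

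**The concern.** Two things combine. First, the no-contact rule puts people who could not be reached together with people who asked not to be contacted, and no reason is given. Someone unreachable around Visit 2 may be reachable at D180, but the protocol tells the site not to try. The memory aid is handed out at Visit 2, so a subject lost before then also lacks the tool meant to support later reporting.

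Second, such a subject stays in the SafAS if any safety data exist, and no minimum follow-up is required. A crude proportion over the SafAS then counts the unobserved months as if nothing happened in them. At stake is a downward bias in the 6-month SAE and MAAE proportions, and a table that does not show how many subjects were actually followed to 6 months.

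**Working it through.** **Inputs from the documents.** 450 planned per group. Visit 2 at D30 to D44. SAE window to D180. A subject last observed at D30 therefore loses 180 − 30 = 150 days, and one last observed at D44 loses 180 − 44 = 136 days.

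**Nearest stated attrition figure.** The Protocol synopsis gives 450 planned and 382 evaluable per group: 1 − 382/450 = 15.1%. This concerns evaluable subjects, not loss to safety follow-up, and the sample-size inputs are redacted. It serves here only as an upper bound on loss.

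**Assumptions (not in the documents).** Proportion lost L = 1% to 15%. Six-month SAE risk in other subjects p = 2% to 4%. Risk in lost subjects k = 1 to 5 times p. Loss at D30 and an even hazard, so the unobserved share is u = 150/180 = 0.833. No SAE after loss is reported by another route.

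**Formulas.**
- True risk = (1 − L)p + Lkp
- Crude SafAS risk = (1 − L)p + Lkp(1 − u)
- Relative shortfall = Lku / [(1 − L) + Lk], in which p cancels

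**Worked case, L = 3%, p = 4%.**
- k = 1: true 4.00%; crude 3.88% + 0.12%/6 = 3.90%; shortfall 0.10 percentage points, or 2.5% relative.
- k = 3: true 3.88% + 0.36% = 4.24%; crude 3.88% + 0.36%/6 = 3.94%; shortfall 0.30 percentage points, or 7.1% relative.

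**Relative shortfall in the SAE proportion.**

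| Lost | k = 1 | k = 3 | k = 5 |
|---|---|---|---|
| 1% | 0.8% | 2.5% | 4.0% |
| 3% | 2.5% | 7.1% | 11.2% |
| 5% | 4.2% | 11.4% | 17.4% |
| 15% | 12.5% | 28.8% | 39.1% |

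**MAAEs from Visit 2 to D180.** A subject lost before Visit 2 contributes no observed time to this window, so u = 1. At L = 3% the shortfall is 3.0% for k = 1, and 0.09/(0.97 + 0.09) = 8.5% for k = 3.

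**Effect of the denominator.** Suppose 14 of 450 subjects in a group have an observed SAE (assumption), none of them among the lost.
- SafAS: 14/450 = 3.11% (Clopper-Pearson 95% CI 1.71 to 5.16).
- 3% lost (14 subjects) removed: 14/436 = 3.21% (1.77 to 5.33).
- 5% lost (22 subjects) removed: 14/428 = 3.27% (1.80 to 5.43).
- Extreme bound, every lost subject with an unreported SAE: (14 + 14)/450 = 6.22% at 3% lost; (14 + 22)/450 = 8.00% at 5% lost.

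**Between groups.** With loss of 3% in one group and 5% in the other, p = 3% and k = 1, the false difference is 3% × 0.833 × 2% = 0.05 percentage points.

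**The case against.** The label comes only after documented calls and certified mail have failed, so a further call may well fail too. If those efforts uncover a hospitalisation or death, the event becomes reportable. The reason for termination may then be SAE, which ranks above lost to follow-up in 5.2.11 and carries full safety follow-up. Subjects are asked about SAEs at the D08 call and are told to report them at any time. Those who complete Visit 2 still have Telephone Call 2 scheduled. The SAP also reports SAEs within 30 days, a window less affected. Safety is descriptive, and the primary immunogenicity analysis is untouched.

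All of this stands, and it limits the point to a small one. It does not remove it. Efforts made around a missed Visit 2 cannot capture what happens in the 136 or more days that follow. Self-report is possible but is not a planned contact.

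A reader might go further and infer that lost subjects' SAEs are missed outright and that each such subject counts as event-free. The documents do not support that: SAEs known before contact ended are kept and counted, later ones can still be self-reported, and a vaccinated subject with no safety data is outside the SafAS. No text says that lost subjects are event-free; the effect follows from using a crude proportion. The no-replacement rule concerns imputation and sets no denominator. A reader might also infer that these are the subjects most likely to have had an event. That is plausible at age 56 and over, but nothing in the documents links loss to SAEs, so k above 1 is an assumption.

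**Conclusion.** The point holds in limited form. For subjects classed as lost to follow-up, the protocol forgoes a contact that it makes for voluntary withdrawals, without a stated reason. Unreported SAEs and MAAEs after last contact can go uncaptured, and the planned proportions in effect treat that time as event-free.

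The bias is downward. At 3% loss it is about 2.5% relative for SAEs if loss is unrelated to risk, and about 7% if lost subjects have three times the risk. In the 14-event illustration, changing the denominator moves the estimate far less than the width of its confidence interval. The bias would matter more only if loss were common or strongly linked to events. The loss rate, SAE risk and risk ratio are all assumed, because the documents give none of them. No hypothesis test or primary conclusion is affected.

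**What to change.** **Protocol 5.2.12.** Delete lost to follow-up from the no-contact sentence, so that the already scheduled Telephone Call 2 (D180 +14 days) is attempted. Keep the rule for subjects who withdrew consent and asked not to be contacted.

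**SAP.** The call alone leaves still-unreachable subjects in the denominator. So state the SAE and MAAE denominators, report the number with completed 6-month contact per group, and add a completed-contact or person-time sensitivity analysis of both event types. SAP 4.4.4.2 already derives duration including follow-up. It takes the latest of last visit, termination form and follow-up contact, so confirm that a late form date does not add unobserved time for lost subjects.

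The sensitivity analysis corrects only for loss unrelated to risk. In the worked case with k = 3, subjects followed to 6 months would show 4.00% against a true 4.24%. The call is therefore worth attempting as well.

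**Cost.** One protocol sentence, one call attempt for each lost subject, one table row and one sensitivity table. The downside is minor site time, with a modest success rate for the calls.
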